9.1. Efficacy Assessments

The following ocular assessments will be done during Part A at the time points listed:

DEQ-5	Screening, Day -1
VAS	Screening, Day -1, Day 1 (0 (predose), 0.5, 1, 2, 4, 8, 12, 24 hours)
OSDI [©]	Screening, Day -1
MMP-9 (InflammaDry)	Screening, Day -1
TFBUT	Screening, Day 1 (0, 2, 12, 24 hours)
Corneal fluorescein staining (Baylor)	Screening, Day -1, Day 1 (0, 2, 12, 24 hours)
Lissamine green staining (Baylor +Lid Margin [lid wiper epitheliopathy])	Screening, Day 1 (0 hour)

The following ocular assessments will be done during Part B at the time points listed:

DEQ-5	Screening, Day -1, Day 29
VAS	Screening, Day -1, Day 1 (0, 0.5, 1, 2, 4, 8, 12 hours), Days 2 and 3 (0, 4, 8, 12 hours), Days 4 and 7 (0, 0.5, 1, 2, 4, 8, 12 hours), Days 5 and 6 (0, 4, 8, 12 hours) Day 8 (0 hour), Days 15, 22 and 29 (0, 4, 8 hours)
OSDI [©]	Screening, Day -1, Days 8, 15, 22 and 29 at 0 hour
MMP-9 (InflammaDry)	Screening, Day -1, and 29 (0 hour)
TFBUT	Screening, Day 1 (0, 2 and 12 hours), Days 2 through 7 (0 and 12 hours) Days 8, 15, 22, and 29 (0 hour)
Corneal fluorescein staining (Baylor)	Screening, Day -1, Day 1 (0, 2 and 12 hours), Days 2 through 7 (0 and 12 hours) Days 8, 15, 22, and 29 (0 hour)

Lissamine green staining (Baylor +Lid Margin [lid wiper epitheliopathy])	Screening, Day 1 (0 and 12 hours), Days 2 through 7 (0 and 12 hours) Days 8, 15, 22, and 29 (0 hour)
---	--

Please note: For Part A and B of this study all OSDI, DEQ-5 and VAS assessments will be completed prior to any laboratory or PK timepoints. TFBUT, Corneal fluorescein staining and Lissamine green staining will be scheduled to be completed following any laboratory or PK timepoints.

9.2. Safety Assessments

Planned time points for all safety assessments are provided in the [SoA](#).

9.2.1. Ocular Safety

The following ocular safety assessments will be conducted during Part A at the time points listed:

Visual acuity (Snellen)	Screening, Day -1, Day 1 (12 and 24 hours)
Slit lamp biomicroscopy (w/out mydriatics)	Screening, Day 1 (0, 1, 2, 12, 24 hours)
Aesthesiometer	Screening
Schirmer I	Screening, Day -1, Day 1 (12 and 24 hours)
VAS with anesthesia	Screening
Intraocular pressure (iCare tonometer)	Screening, Day 1 (0, 2, 12, 24 hours)
Slit lamp biomicroscopy (w/ mydriatics; lens observation)	Screening, Day -1, Day 1(12 and 24 hours)
Ophthalmoscopy	Screening, Day -1, Day 1(12 and 24 hours)

The following ocular safety assessments will be conducted during Part B at the time points listed:

Visual acuity (Snellen)	Screening, Day -1, Day 1 (12 hours), Days 2 through 8, 15, 22, and 29 (0 hour)
Slit lamp biomicroscopy (w/out mydriatics)	Screening, Day 1 (0, 1, 2, 12 hours), Days 2 through 7 (0 and 12 hours), Days 8, 15, 22, and 29 (0 hour)
Aesthesiometer	Screening
Schirmer I	Screening, Day -1, Day 1 (12 hours), Days 2, 8 and 29 (0 hour)

VAS with anesthesia	Screening
Intraocular pressure (iCare tonometer)	Screening, Day 1 (0 and 12 hours), Days 2, 3, 8, 15, 22, and 29 (0 hour)
Slit lamp biomicroscopy (w/ mydriatics; lens observation)	Screening, Day -1, Day 1 (12 hours), Days 8 and 29 (0 hour)
Ophthalmoscopy	Screening, Day -1, Day 1 (12 hours), Days 8 and 29 (0 hour)

Please note: For Part A and B of this study, all ocular safety assessments will be scheduled to be performed following laboratory and PK time points.

9.2.2. Physical Examinations

A complete physical examination will include, at a minimum, assessments of HEENT, the Cardiovascular, Respiratory, Gastrointestinal, Dermatologic, and Neurologic systems. Height and weight will also be measured and recorded.

Investigators should pay special attention to clinical signs related to previous serious illnesses.

9.2.3. Vital Signs

Vital signs will be measured in a semi-supine position after 5 minutes rest and will include oral body temperature, systolic and diastolic blood pressure, heart rate, and respiratory rate. Vital signs will be measured before collection of blood samples for laboratory tests or PK.

9.2.4. Clinical Safety Laboratory Assessments

See [Appendix 2](#) for the list of clinical laboratory tests to be performed and to the [SoA](#) for the timing and frequency.

The investigator must review the laboratory report, document this review, and record any clinically relevant changes occurring during the study in the AE section of the CRF. The laboratory reports must be filed with the source documents. Clinically significant abnormal laboratory findings are those which are not associated with the underlying disease, unless judged by the investigator to be more severe than expected for the subject's condition.

All laboratory tests with values considered clinically significantly abnormal during participation in the study should be repeated until the values return to normal or baseline or are no longer considered clinically significant by the investigator or medical monitor.

- If such values do not return to normal/baseline within a period of time judged reasonable by the investigator, the etiology should be identified and the sponsor notified.
- All protocol-required laboratory assessments, as defined in [Appendix 2](#), must be conducted in accordance with the laboratory manual and the [SoA](#).
- If laboratory values from non-protocol specified laboratory assessments performed at the institution's local laboratory require a change in subject management or are considered clinically significant by the investigator (eg, SAE or AE or dose modification), then the results must be recorded in the CRF.

9.3. Adverse Events

The definitions of an AE or SAE can be found in [Appendix 4](#).

AEs will be recorded from the beginning of the run-in phase. Any medical occurrence before run-in will be recorded as medical history. AE will be reported by the subject (or, when appropriate, by a caregiver, surrogate, or the subject's legally authorized representative).

The investigator and/or designees are responsible for detecting, documenting, and recording events that meet the definition of an AE or SAE and remain responsible for following up AEs that are serious, considered related to the study treatment or study procedures, or that caused the subject to discontinue the study (see [Section 8](#)).

9.3.1. Time Period and Frequency for Collecting AE and SAE Information

All SAEs will be collected from the beginning of the run-in phase to the follow-up visit.

Medical occurrences that begin before the start of study treatment but after obtaining informed consent will be recorded on the Medical History/Current Medical Conditions section of the case report form (CRF) not the AE section.

All SAEs will be recorded and reported to the sponsor or designee within 24 hours, as indicated in [Appendix 4](#). The investigator will submit any updated SAE data to the sponsor within 24 hours of it being available.

Investigators are not obligated to actively seek AE or SAE in former study subjects. However, if the investigator learns of any SAE, including a death, at any time after a subject has been discharged from the study, and he/she considers the event to be reasonably related to the study treatment or study participation, the investigator must promptly notify the sponsor.

The method of recording, evaluating, and assessing causality of AE and SAE and the procedures for completing and transmitting SAE reports are provided in [Appendix 4](#).

9.3.2. Method of Detecting AEs and SAEs

Care will be taken not to introduce bias when detecting AEs and/or SAEs. Open-ended and non-leading verbal questioning of the subject is the preferred method to inquire about AE occurrences.

9.3.3. Follow-up of AEs and SAEs

After the initial AE/SAE report, the investigator is required to proactively follow each subject at subsequent visits/contacts. All SAEs, will be followed until resolution, stabilization, the event is otherwise explained, or the subject is lost to follow-up (as defined in [Section 8.3](#)). Further information on follow-up procedures is given in [Appendix 4](#).

9.3.4. Regulatory Reporting Requirements for SAEs

- Prompt notification by the investigator to the sponsor of a SAE is essential so that legal obligations and ethical responsibilities towards the safety of subjects and the safety of a study treatment under clinical investigation are met.
- The sponsor has a legal responsibility to notify both the local regulatory authority and other regulatory agencies about the safety of a study treatment under clinical investigation. The sponsor will comply with country-specific regulatory requirements relating to safety reporting to the regulatory authority, Institutional Review Boards (IRB)/Independent Ethics Committees (IEC), and investigators.
- Investigator safety reports must be prepared for suspected unexpected serious adverse reactions (SUSAR) according to local regulatory requirements and sponsor policy and forwarded to investigators as necessary.
- An investigator who receives an investigator safety report describing a SAE or other specific safety information (eg, summary or listing of SAEs) from the sponsor will review and then file it along with the Investigator's Brochure and will notify the IRB/IEC, if appropriate according to local requirements.

9.3.5. Pregnancy

- Details of all pregnancies in female subjects and, if indicated, female partners of male subjects will be collected after the start of study treatment and until termination or 8 weeks after birth.
- If a pregnancy is reported, the investigator should inform the sponsor within 24 hours of learning of the pregnancy and should follow the procedures outlined in [Appendix 5](#).

- Abnormal pregnancy outcomes (eg, spontaneous abortion, fatal death, stillbirth, congenital anomalies, ectopic pregnancy) are considered SAEs.

9.4. Treatment of Overdose

An overdose occurring from topical administration of SJP-0132 ophthalmic [REDACTED] is unlikely but in the case of a suspected overdose, the subject will be instructed to contact the investigator or study coordinator immediately. General support measures should be used in the case of excessive pharmacological effects or overdose. No antidotes are available.

9.5. Pharmacokinetics

Blood samples will be collected for measurement of plasma concentrations of SJP-0132 as specified in the SoA. Additional samples may be collected at additional time points during the study if warranted and agreed upon between the investigator and the sponsor. Instructions for the collection and handling of biological samples will be detailed in a protocol specific lab manual. The actual date and time (24-hour clock time) of each sample will be recorded.

Samples will be used to evaluate the PK of SJP-0132. Samples collected for analyses of SJP-0132 plasma concentration may also be used to evaluate safety or efficacy aspects related to concerns arising during or after the study.

Drug concentration information that would unmask the study will not be reported to the Investigator or masked personnel until the study has been unmasked.

Any changes in the timing or addition of time points for any planned study assessments must be documented and approved by the relevant study team member and then archived in the sponsor and site study files, but will not constitute a protocol amendment. The IRB/IEC will be informed of any safety issues that require alteration of the safety monitoring scheme or amendment of the ICF.

The following PK parameters for SJP-0132 will be estimated using actual sample collection times:

C_{\max}	maximum plasma concentration
$C_{\max,\text{norm}}$	C_{\max} divided by dose per body weight
C_{trough}	minimum (predose) plasma concentration during repeat dosing
t_{\max}	time to reach the maximum plasma concentration
t_{last}	time to last quantifiable concentration
$AUC_{0-\text{last}}$	area under the plasma concentration-time curve from time 0 to time of the last quantifiable concentration
$AUC_{0-\infty}$	area under the plasma concentration-time curve from time 0 to infinite time, calculated as the sum of $AUC_{0-\text{last}}$ and $C_{\text{last}}/\lambda_z$, in which C_{last} is the last observed quantifiable concentrations
$AUC_{0-\text{last},\text{norm}}$	$AUC_{0-\text{last}}$ divided by dose per body weight
$AUC_{0-\infty,\text{norm}}$	$AUC_{0-\infty}$ divided by dose per body weight

AUC% _{extrap}	percentage of AUC _{0-∞} that is due to extrapolation beyond t _{last}
AUMC _{0-last}	area under the moment curve from time 0 to time of the last quantifiable concentration
AUMC _{0-∞}	area under the moment curve from time 0 to infinite time
MRT _{0-last}	mean residence time from time 0 to time of the last quantifiable concentration
MRT _{0-∞}	mean residence time from time 0 to infinite time
t _{1/2}	elimination half-life associated with the terminal slope ($λ_z$) of the semilogarithmic drug concentration-time curve, calculated as $0.693/λ_z$
Vd/F	apparent volume of distribution
CL/F	apparent total body clearance
R _{ac}	accumulation ratios calculated as (C _{trough} on day 4) / (C _{trough} on day 2) and (C _{trough} on day 8) / (C _{trough} on day 2) (Part B)

9.6. Health Economics

No Health Economic information will be collected.

10. Statistical Considerations

10.1. General Considerations

The primary statistical analysis of the data will be descriptive in nature. For continuous variables this means calculation of the number of observations, mean, standard deviation, median, minimum, and maximum. Categorical variables will be summarized by subject counts and related percentages. For ordinal-scaled variables, a combination of the above may be employed as appropriate: frequency and percentage of observations within a category and means and standard deviations of the scores of the categories. For categorical and ordinal variables, percentages will be calculated based on non-missing data.

10.2. Sample Size Determination

No formal sample size and/or power calculations were performed for the study, however a sample size was chosen based on feasibility to allow total of 92 randomized subjects for Part A (n=32) and Part B (n=60). Approximately 32 subjects are expected to complete Part A and 60 subjects are expected to complete Part B.

10.3. Populations for Analyses

For purposes of analysis, the following populations are defined:

Population	Description
Enrolled	Consist of all enrolled subjects. Subjects who signed the ICF. This population will be used in disposition outputs
Safety set	All subjects randomly assigned to study treatment and who take at least 1 dose of study treatment. Subjects will be analyzed according to the treatment they actually received. It will be the primary population for the safety and tolerability analysis.
Full analysis set	All subjects randomly assigned to study treatment and who take at least 1 dose of study treatment and have a post-baseline efficacy measurement. Subjects will be analyzed according to the treatment they actually received.
Per protocol set	All subjects who completes the study with at least 75% overall dosing compliance and without any other major protocol deviations/violations.
Pharmacokinetic set	All subjects who take at least 1 dose of active drug and have at least 1 quantifiable plasma concentration collected postdose without important protocol deviations/violations or events thought to significantly affect the PK.

10.4. Statistical Analyses

All the analysis will be carried out separately for Part A and Part B upon completion of the study visit (EOS). Data will be summarized by cohort and across all active dose levels. Complete details of the statistical analyses to be performed will be documented in a statistical analysis plan, which will be completed prior to database lock. This document will include more detail of analysis populations, summary strategies, and any amendments to the proposed analyses listed here, if necessary. Any changes to the statistical analysis plan will be outlined in the final study report.

10.4.1. Efficacy Analyses

This section is a summary of the planned statistical analyses of the primary and secondary endpoints. All analyses, summaries, and listings will be performed using SAS® software (Version 9.4 or higher version)

Endpoint	Statistical Analysis Methods
Primary	
Change from baseline (predose on Day 1) in eye dryness symptom (visual analog scale [VAS]) at 4 hours on Day 29
 
Change from baseline (predose on Day 1) in corneal fluorescein staining (CFS) score at the central zone on Day 29

Secondary	
Changes from baseline in dry eye signs: CFS scores at the central, superior, inferior, nasal, temporal and total zones, conjunctival lissamine green staining (CLGS) scores at each of 3 nasal and 3 temporal zone and total zone of bulbar conjunctiva, lid wiper epitheliopathy score, and tear film break-up time (TFBUT) at each time point tested
 
Changes from baseline in dry eye symptoms (VAS [ie, severity of eye dryness, discomfort, burning/stinging, sticky feeling, foreign body sensation, itching, pain, blurred vision, and sensitivity to light], ocular surface disease index [OSDI®], Dry eye Questionnaire 5 [DEQ-5] scores) at each time point tested
 
Biomarker (Matrix Metalloproteinase-9 (MMP-9), InflammaDry®)

The study eye will be the eye with the greater central zone corneal fluorescein staining score at predose on Day 1. If both eyes meet all of the inclusion and none of the exclusion criteria and the central zone corneal fluorescein staining scores are equal, the right eye (OD) will be designated as the study eye for the duration of this study.

The fellow eye (non-study eye) will be treated with the product as per the assigned dosing schedule.

Change in eye assessments will be summarized using descriptive statistics (mean, standard deviation, coefficient of variation (%CV), median, minimum, and maximum).

For this study co-primary endpoints will be as follows: the differences between SJP-0132 and placebo in changes from baseline in eye dryness symptom (visual analog scale [VAS]) and change from baseline (predose on Day 1) in corneal fluorescein staining (CFS) score at the central zone on Day 29.

Secondary endpoints are changes from baseline in dry eye signs: CFS scores at the superior, inferior, nasal, temporal and total zones, conjunctival lissamine green staining (CLGS) scores at each of 3 nasal and 3 temporal zone and total zone of bulbar conjunctiva, lid wiper epitheliopathy score, and tear film break-up time (TFBUT) at each time point tested. Changes from baseline in dry eye symptoms (VAS [ie, severity of eye dryness, discomfort, burning/stinging, sticky feeling, foreign body sensation, itching, pain, blurred vision, and sensitivity to light], ocular surface disease

index [OSDI[®]], Dry eye Questionnaire 5 [DEQ-5] scores) at each time point tested and Biomarker (Matrix Metalloproteinase-9 (MMP-9), InflammaDry[®]).

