Part B: 2 cohorts consisting of 30 subjects each (9 Japanese and 21 non-Japanese) 20 randomized to SJP-0132 ophthalmic [REDACTED] and 10 randomized to placebo

Cohort#	Active		Placebo		Total
	JP	Non-JP	JP	Non-JP	
5	6	14	3	7	30
6	6	14	3	7	30
Total	12	28	6	14	60

JP = Japanese

For Part A, subject participation will be approximately 32 days, including Screening. For Part B, subject participation will be approximately 9 weeks, including Screening. Total study duration is anticipated to be 3 months.

Investigational Product, Dose, and Mode of Administration

One drop of SJP-0132 ophthalmic [REDACTED] instilled in both eyes [REDACTED]

Statistical Methods

The primary statistical analysis of the data will be descriptive in nature. For continuous variables this means calculation of the number of observations, mean, standard deviation, median, minimum, and maximum. Categorical variables will be summarized by subject counts and related percentages. For ordinal-scaled variables, a combination of the above may be employed as appropriate: frequency and percentage of observations within a category and means and standard deviations of the scores of the categories. For categorical and ordinal variables, percentages will be calculated based on non-missing data.

Sample Size Determination:

No formal sample size and/or power calculations were performed for the study, however a sample size was chosen based on feasibility to allow total of 92 randomized subjects for Part A (n=32) and Part B (n=60). Approximately 32 subjects are expected to complete Part A and 60 subjects are expected to complete Part B.

Safety Analysis:

Safety assessments and changes from baseline in vital signs, clinical laboratory results, adverse events (AEs), will be summarized using descriptive statistics (mean, standard deviation, coefficient of variation (%CV), median, minimum, and maximum). Concomitant medications and physical examination findings will be listed.

Efficacy Analysis:

The study eye will be the eye with the greater central zone corneal fluorescein staining. If both eyes meet all of the inclusion and none of the exclusion criteria and the central zone corneal fluorescein staining scores are equal, the right eye (OD) will be designated as the study eye for the duration of this study.

The fellow eye (non-study eye) will be treated with the product as per the assigned dosing schedule.

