6.1. Inclusion Criteria

Subjects are eligible to be included in the study only if all of the following criteria apply:

1. Signed the informed consent form which includes compliance with the requirements and restrictions listed in the informed consent form (ICF) and in this protocol
2. Man or woman, ≥ 18 years of age (inclusive) at the time of signing the informed consent form
3. Body mass index (BMI) within 18.5 to 30.0 kg/m^2 (inclusive) and body weight between 45 kg and 100 kg
4. Generally healthy as determined by medical history, physical examinations, clinical laboratory examination, and ophthalmologic examinations performed at Screening.
5. Have a subject reported history of Dry Eye Disease in both eyes for at least 6 months prior to Screening.
6. Dry eye symptoms at Screening and Day -1:
 - Baseline eye dryness VAS score ≥ 40 mm
 - Baseline DEQ 5 ≥ 6
7. Dry eye signs at Screening and Day -1:
 - Baseline central corneal staining (Baylor scale) of 2 to 4 in at least 1 eye (designated study eye)
8. Non-smoker or ex-smoker for > 12 months
9. If male, must agree to use contraception during the treatment period and for at least 7 days, after the last dose of study treatment and refrain from donating sperm during this period
10. If a woman of child-bearing potential (WOCBP), she must agree to use a highly effective form of contraception during the study and for 30 days after the last dose.
11. For Japanese cohort subjects, subjects must be of Japanese descent.

Note: Retesting of abnormal lab values that may lead to exclusion will be allowed once. Retesting will take place during an unscheduled visit in the screening phase.

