- MMP-9 (30 minutes before TFBUT and staining tests)
- TFBUT

- Corneal fluorescein staining (Baylor)
- Lissamine green (Baylor + Lid Margin)
- Aesthesiometer
- Schirmer I without anesthesia
- VAS with anesthesia
- Intraocular Pressure (iCare tonometer)
- Slit lamp biomicroscopy (w/ mydriatics; lens observation)
- Ophthalmoscopy

Run-in (Day -14 +2 to Day -2)

- Educate subject in self-administration and dosing diary completion
- Dispense placebo. Subjects will instill one drop in each eye [REDACTED] (First dose may be administered in office as part of self-administration education, if visit is completed on Day -14, otherwise subject should be instructed to begin dosing on Day -14)
- Review AEs and concomitant medications

Day -1 (Check-in)

- Review medical and medication history
- Review inclusion/exclusion criteria
- Weight
- Vital signs
- DEQ-5
- VAS
- OSDI
- Clinical laboratory tests (hematology, serum chemistry, urinalysis)
- Urine drug and alcohol screens
- Urine pregnancy test for WOCBP
- Visual acuity (Snellen)
- MMP-9 (30 minutes before staining tests)
- Corneal fluorescein staining (Baylor)
- Schirmer I without anesthesia
- Slit lamp biomicroscopy (w/ mydriatics; lens observation)
- Ophthalmoscopy

- Review AEs and concomitant medications
- Administer placebo [REDACTED] as during run-in

Day 1, Predose

- Review AEs and concomitant medications
- Physical examination
- Vital signs
- VAS
- PK sampling
- Slit lamp biomicroscopy (without mydriatics)
- TFBUT
- Corneal fluorescein staining (Baylor)
- Lissamine green (Baylor + Lid Margin) at 12 hours
- Intraocular Pressure (iCare tonometer)
- Randomize to study treatment

Day 1, 0 hour

- Administer study drug

Day 1, Postdose

- Review AEs and concomitant medications
- Physical examination at 1 hour
- Vital signs at 0.5, 1, 2, 4, 8, and 12 hours
- VAS at 0.5, 1, 2, 4, 8, and 12 hours
- PK sampling at 0.25, 0.5, 1, 2, and 4 hours
- Visual acuity at 12 hours
- Slit lamp biomicroscopy (without mydriatics) at 1, 2, and 12 hours
- TFBUT at 2 and 12 hours
- Corneal fluorescein staining (Baylor) at 2 and 12 hours
- Lissamine green (Baylor + Lid Margin) at 12 hours
- Schirmer I without anesthesia at 12 hours
- Intraocular Pressure (iCare tonometer) at 12 hours
- Slit lamp biomicroscopy (w/ mydriatics; lens observation) at 12 hours

- Ophthalmoscopy at 12 hours
- Administer study drug at 4, 8, and 12 hours

Days 2 and 3

- Review AEs and concomitant medications
- Physical examination at 0 hour

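### The study eye is chosen on the same Day 1 predose staining score that serves as the co-primary baseline, and this rule conflicts with inclusion criterion 7

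*Combined protocol and SAP*

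**What the plan says.** Three places in the protocol define the study eye.

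- **Section 6.1, criterion 7.** Under the lead-in "Dry eye signs at Screening and Day -1", it requires "Baseline central corneal staining (Baylor scale) of 2 to 4 in at least 1 eye (designated study eye". The label goes to an eye that qualified at those two visits.
- **Section 10.4.1.** "The study eye will be the eye with the greater central zone corneal fluorescein staining score at predose on Day 1". Qualification appears only in the tie-break: if both eyes qualify and the scores are equal, the right eye is used. Nothing limits the main rule to qualifying eyes, and nothing covers a tie when one eye qualified.
- **Synopsis, Efficacy Analysis.** "The study eye will be the eye with the greater central zone corneal fluorescein staining", with no visit named.

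The CFS co-primary endpoint is "Change from baseline (predose on Day 1) in corneal fluorescein staining (CFS) score at the central zone on Day 29", so the reading that selects the eye is also the baseline. On reporting, "Change in eye assessments will be summarized using descriptive statistics" (Section 10.4.1) and "Data will be summarized by cohort and across all active dose levels" (Section 10.4).

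**The concern.** There are two separate problems.

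**Which eye is analysed.** If only one eye met criterion 7 and the other eye scores higher on Day 1, criterion 7 and Section 10.4.1 name different eyes. Two programmers could derive different study-eye variables from the same data, and a subject could enter on one eye and be analysed on the other. The label also matters for safety data. Appendix 4 requires ocular adverse events to be attributed to the study or fellow eye, and Section 9.3 records events from the start of run-in. Under Section 10.4.1 the study eye is not known until Day 1 predose.

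**Regression to the mean.** The higher of two readings is, on average, the one with the more positive error. When it is also the baseline, the Day 29 score tends to fall back with no real change. Within-arm mean changes in a co-primary endpoint are reported descriptively, so this artefact can be read as improvement.

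**Working it through.** The documents give no SD, reading reliability, between-eye correlation or power calculation (Section 10.2 says none was done). There is no stated figure to reproduce, and everything numerical below rests on assumed inputs. Negative values mean apparent improvement.

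**1. Closed form for the mechanism.** Take continuous scores, no eligibility filter and errors independent between eyes. Let s_e be the SD of reading error and s_w the SD of an eye's true score around its subject's mean. The expected error in the selected baseline is

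s_e² / √(π(s_e² + s_w²)).

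- s_e = s_w = 0.5: 0.25 / √(π × 0.5) = 0.25 / 1.253 = 0.20.
- s_e = 0.25, s_w = 1.0: 0.0625 / √(π × 1.0625) = 0.03.
- s_e = 0.75, s_w = 0.25: 0.5625 / √(π × 0.625) = 0.40.

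The value is positive whenever readings vary. Error shared by both eyes does not affect which eye is chosen, so correlated errors reduce it.

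**2. Simulation with criterion 7 applied.** Assumed: whole grades 0-4, true mean 1.6, SD 0.9, between-eye true correlation 0.6-0.8, reading-error SD 0.4-0.8, no true change. Eligible subjects have at least one eye scoring 2-4 at both Screening and Day -1. Under the rule as written, a Day 1 tie goes to the only qualifying eye, otherwise to the right eye. With errors independent across visits, the shift in mean change is:

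| Rule | Errors independent between eyes | Between-eye error correlation 0.5-0.8 |
|---|---|---|
| 10.4.1 as written | -0.12 to -0.37 | -0.06 to -0.24 |
| Higher Day 1 score, qualifying eyes only | -0.09 to -0.17 | -0.05 to -0.14 |
| Higher Day -1 score, qualifying eyes only | within 0.01 of zero | within 0.01 of zero |
| Higher mean of Screening and Day -1, qualifying eyes only | within 0.01 of zero | within 0.01 of zero |

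Under 10.4.1 as written, the analysed eye had not met criterion 7 in 3-14% of subjects (independent) or 0.4-8% (correlated).

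**3. Scale against sampling error.** The SD of change under the written rule is 0.67-1.15. For the 20 active subjects per Part B cohort (Section 7.5), the standard error is 0.67/√20 = 0.15 to 1.15/√20 = 0.26. Setting by setting, the shift is 0.8-1.5 standard errors (independent) or 0.4-0.9 (correlated).

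**4. Sensitivity.**

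- True mean 1.2-2.0 and SD 0.7-1.1: shift -0.10 to -0.40 (independent) and -0.04 to -0.26 (correlated); non-qualifying eye 2-20% and 0.2-12%.
- A different model (0-6 scale, true mean 2.2, between-subject SD 0.8, s_e 0.25-0.75, s_w 0.25-1.0): shift -0.07 to -0.41; non-qualifying eye 6-22%.
- Day -1 and Day 1 errors correlated at 0.5, in the model of step 2: -0.09 to -0.44 as written, -0.08 to -0.32 for Day 1 limited to qualifying eyes, -0.04 to -0.21 for the Day -1 rule.

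**5. Treatment contrast.** In Section 9, Part B, Day 1 Predose, "Randomize to study treatment" is the last item, after the CFS reading, so selection acts equally on both arms. With no true effect, the simulated active-minus-placebo difference is within 0.01 of zero. With a true effect of -0.50 in the 0-6 model (s_e = s_w = 0.5), the mean changes are -0.72 active and -0.23 placebo. The difference is -0.50, although the active change alone overstates the effect.

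**The case against.** The strongest reply is that the co-primary is defined as a difference from placebo, and that difference is unbiased. In a descriptive Phase 1/2 study with concurrent placebo, the same shift shows in the placebo arm. This is right, and it limits the harm to within-arm and by-cohort summaries and to which eye is analysed.

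Second, Sections 6.1 and 10.4.1 can be read together as meaning the worse qualifying eye, since the tie-break refers to qualification. That reading is reasonable, and under it no non-qualifying eye is analysed. But the text does not say it, and with independent visit errors a shift of -0.05 to -0.17 remains.

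Third, both eyes are treated and examined, and criterion 5 requires a history of dry eye in both. Analysing the other eye is therefore not analysing an untreated or healthy one, and either rule can be applied to the data collected. This softens the consequence but leaves the rule undefined.

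Fourth, every input to the size is assumed and the ranges are wide. That stands: the direction is secure, the size is not. The remedy is also partial if errors one day apart are correlated, and some of what remains comes from the Day -1 eligibility threshold, which no study-eye rule removes.

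Finally, Section 10.4 defers detail to a later SAP. That could settle the matter, but it does not reconcile two rules the protocol already states.

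**Conclusion.** The concern holds and should be corrected. The conflict between criterion 7 and Section 10.4.1 is in the text and needs no assumption. The shift of within-arm CFS change toward improvement follows whenever readings contain error that the two eyes do not share. Confidence is high for both, and low for the size: roughly 0.1 to 0.4 grade under the written rule if errors are independent between eyes, less if they are correlated, on an assumed 0-4 scale with no true change. Real change over four weeks would add to or offset this. The comparison with placebo is not biased.

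**What to change.** Put one study-eye rule in the synopsis, Section 6.1 and Section 10.4.1:

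- Choose only among eyes that met criterion 7.
- Use central CFS read before Day 1: the Day -1 score, or the mean of Screening and Day -1. Day -1 alone is preferable because Screening precedes the placebo run-in.
- If tied, use the right eye.
- Use Day 1 predose only as the baseline value.

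The sponsor should also clarify whether criterion 7 requires the same eye to qualify at both visits. No new eligibility rule is proposed. If different eyes may qualify, choosing the higher Day -1 score still leaves a shift within 0.01 of zero when visit errors are independent.

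If the Day 1 rule is kept, limit it to eyes that met criterion 7 and state in the report that within-arm CFS change includes this shift.

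**Cost.** Only wording changes: Section 9.1 already schedules CFS at Screening and Day -1, and Section 5.1 has both eyes examined. Under the step 2 assumptions with independent visit errors, the Day -1 rule raises the share of study eyes with a Day 1 baseline below 2 from 6-11% to 11-23% (from 7-17% to 10-22% with correlated between-eye errors), leaving less room to improve. The SD of change rises by at most about 6%. If Day -1 and Day 1 errors correlate at 0.5, a shift of -0.04 to -0.21 remains.
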